6. DOSING DELAYS AND MODIFICATIONS

Patients will be monitored closely for toxicity, and the axitinib dose may be adjusted according to individual patient tolerance.

Table 2: Suggested Dose Modification Algorithms for Potential Treatment-Related Adverse Events

AE Terms & Descriptions	Dose Modification Algorithms
Hypertension	
(A). Hypertension: If persistent hypertension occurs despite antihypertensive medications, reduce dose; discontinue if hypertension is severe and persists despite dose reduction	Step 1. Continue investigational product (IP) at the current dose. Step 2. Adjust current or initiate new antihypertensive medication(s). Step 3. Titrate antihypertensive medication(s) during next 2 weeks as indicated to achieve well-controlled ^a blood pressure (BP). If BP is not well-controlled within 2 weeks, consider referral to a specialist and go to scenario (B).
(B). Hypertensive crisis:	Discontinue Axitinib
(C). Hemorrhage	If any bleeding requires medical intervention, temporarily interrupt axitinib dose.
(D). Reversible posterior leukoencephalopathy syndrome:	Discontinue axitinib
(E) Moderate-to-severe proteinuria	Reduce dose or temporarily interrupt treatment
(F) Strong CYP3A 4/5 inhibitors:	Avoid coadministration if possible, if axitinib must be coadministered, decrease dose by ~50% and then adjust according to safety and tolerance; if strong CYP3A4/5 inhibitor is discontinued, may increase to prior axitinib dose after waiting 3-5 half-lives of the inhibitor
(G) Renal Impairment	Based on population pharmacokinetic analyses, no significant difference in clearance observed in patients with pre-existing mild-to-severe renal impairment
(H) Hepatic Impairment	Mild (Child-Pugh A): No adjustment of initial dose is required Moderate (Child-Pugh B): Decrease initial dose by ~50%; subsequent doses can be increased or decreased based on individual safety and tolerability Severe (Child-Pugh C): Has not been studied

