4.1 Axitinib Administration

Pfizer will supply Axitinib and it will be shipped in labeled boxes, with unlabeled bottles inside. The pharmacy must have labeling capabilities and fax all requests to Pfizer using the Drug Supply Request Form. Contact information is as follows:

[name], CCRC
[contact]
[contact]
[contact]

Pfizer will be provided with detailed mailing instructions, address/location of Pharmacy, Pharmacist in charge, or anything else that may be helpful for shipping.

Treatment will be administered on an outpatient basis. Axitinib will be initially dosed at 5 mg po BID with or without food. Patients tolerating axitinib at week 4 with no more than grade 2 toxicity and blood pressure controlled to $< 140/90$ mmHg (medication permitted) will have axitinib dose increased to 7mg BID. Axitinib will be dosed for a total of 8-10 weeks.

Swallow axitinib whole with a glass of water; do not split, crush, or chew. If the patient vomits

or misses a dose, an additional dose should not be taken; the next prescribed dose should be taken at the usual time

No investigational or commercial agents or therapies other than axitinib may be administered with the intent to treat the patient's malignancy.

Axitinib should be held for 1 day prior to surgery.

No axitinib will be administered after nephrectomy for any patient.

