5. STUDY CALENDAR

	≤ 4 weeks prior to dosing	Baseline	Day 14 (± 3 days)		Day 28 (± 3 days)	End of Cycle (Day 58 ± 3 days)	End of Treatment ¹
Informed Consent	X						
Vital Signs/ECOG	X	X	X		X	X	X
History / Physical	X	X	X		X	X	X
Hematology ²	X	X*	X		X	X	X
Chemistries ³	X	X*	X		X	X	X
Coagulation ⁴	X					X	
Pregnancy Test ⁵	X						
Urinalysis ⁶	X				X	X	X
Drug Related AE's		X	X		X	X	X
TSH, T3, T4	X					As clinically indicated	X
Axitinib**		X-----X					
Tumor Imaging ⁷	X				X	X	

* Cycle 1, day 1 labs need not be repeated if done within 14 days. ;** Nephrectomy will be performed ≥ 1 days after the last dose of Axitinib

Footnotes for Schedule of Events

1. End of Treatment/Withdrawal: These assessments will occur at least 30 days after nephrectomy date.
2. Hematology: CBC with differential, platelets
3. Blood Chemistry: Albumin, total bilirubin, bicarbonate, BUN, calcium, chloride, creatinine, glucose, magnesium, phosphorus, potassium, SGOT [AST], SGPT [ALT], sodium, ALP, LDH (baseline only).
4. Coagulation: PT/INR and PTT
5. Pregnancy Test: Serum or urine test must be performed for all women of childbearing potential.
6. Urinalysis: with 24 hour urine to ensure protein < 2 grams for anyone with 2+ or greater protein on urinalysis.
7. Tumor Imaging: CT or MRI scan of the chest, abdomen and pelvis (with IV contrast, if possible) to be performed to assess disease status at screening, prior to nephrectomy and whenever disease progression is suspected. CT or MRI scan of the chest is optional at day 28 based on symptoms or pre-enrollment findings. CNS and bone imaging needed only if clinical signs/symptoms are suggestive. Follow up imaging after nephrectomy at the discretion of the treating MD and not part of this protocol.

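### Table 2 row (A) gives dose reduction for hypertension that persists on antihypertensives, but its Step 3 omits the reduction and routes the patient to the crisis row, where the only action is to stop axitinib

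*Protocol*

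**What the plan says.** All the conflicting text is in Protocol section 6, Table 2.

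- **Row (A), left cell:** "If persistent hypertension occurs despite antihypertensive medications, reduce dose; discontinue if hypertension is severe and persists despite dose reduction".
- **Row (A), algorithm cell:** Step 1 keeps the current dose, Step 2 adjusts or starts antihypertensives, and Step 3 titrates them over two weeks. Step 3 then ends: "If BP is not well-controlled within 2 weeks, consider referral to a specialist and go to scenario (B").
- **Row (B):** labelled ("B). Hypertensive crisis", with one action, to discontinue axitinib.

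The same column does state reductions for other problems. Row (E), on proteinuria, reads "Reduce dose or temporarily interrupt treatment". Row (H), on moderate hepatic impairment, reads "Decrease initial dose by ~50" percent. The table's title calls the algorithms suggested, and the section opens by saying that "the axitinib dose may be adjusted according to individual patient tolerance".

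**The concern.** The two cells of one row should describe the same management, and they do not. For a patient whose blood pressure stays high after two weeks of titration but who is not in crisis, the left cell tries a lower dose first. The algorithm cell skips that step and lands in a row written for an emergency.

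The event is foreseeable. Section 2.4.2 lists hypertension among the most common axitinib events, and section 2.4.3 names it among the most common in the earlier neoadjuvant axitinib trial. Treatment here is one short course meant to make partial nephrectomy possible. Section 4.3 says that radical nephrectomy is offered if axitinib does not achieve this, and section 4 enrols only patients whom radical nephrectomy would leave with severe CKD. Ending the course without trying a lower dose is therefore not trivial for the patient concerned. Sites that read different cells could also manage the same patient differently.

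**Working it through.** The protocol gives no figure to reproduce. The check is a side-by-side reading, followed by one illustration of size.

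**1. One patient traced through both cells.** Hypertension, no crisis, not well controlled after two weeks of antihypertensive titration:

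| Source | Next action | When axitinib stops |
|---|---|---|
| Row (A), left cell | Reduce the dose | Severe hypertension continuing after the reduction |
| Row (A), Step 3, then row (B) | Discontinue | At once, with no reduction tried |

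**2. A softer reading of Step 3.** Suppose the referral to row (B) only means that the site should check for crisis. The algorithm cell then gives a patient without crisis no dose action at all. Row (A) needs correcting on either reading.

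**3. Search for a rule that settles it.** Section 4.1 uses blood pressure only as a condition for raising the dose at week 4: "Patients tolerating axitinib at week 4 with no more than grade 2 toxicity and blood pressure controlled to" below 140/90 mmHg. Section 4.3 stops treatment for unacceptable adverse events without defining them. Section 8.3 refers only to unacceptable toxicity. No other row of Table 2 covers persistent hypertension short of crisis.

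**4. Illustration of treatment lost.** Inputs: a planned course of 8 to 10 weeks, or 56 to 70 days (section 4.1); on-treatment vital signs at days 14 and 28 and at "End of Cycle (Day 58 ± 3 days"), with ±3 days on each (section 5). The formula is (planned days − stopping day) / planned days. The start of antihypertensive treatment is assumed.

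- First treated day 14, stopped day 28: (56 − 28)/56 = 28/56 = 50%; (70 − 28)/70 = 42/70 = 60%.
- Day-14 visit held on day 11, stopped day 25: 31/56 = 55%; 45/70 = 64%.
- Day-14 visit held on day 17, stopped day 31: 25/56 = 45%; 39/70 = 56%.
- First treated day 28, next scheduled reading day 58: 0/56 = 0%; 12/70 = 17%.
- The same, with the last visit held on day 55: 1/56 = 2%; 15/70 = 21%.

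Unscheduled readings could move these further. They describe assumed patients and are not bounds.

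**5. Dose at the decision point.** If the control standard in row (A) is at least as strict as that in section 4.1 (an assumption), a patient uncontrolled at day 28 cannot have been escalated and is on at most 5 mg BID. A reduction step therefore needs a level below 5 mg BID.

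**The case against.** The strongest reply is that this is a wrong cross-reference in advisory guidance. A non-crisis patient does not meet the label of row (B), the left cell of row (A) is the only text that names this patient and gives a dose action, and section 6 allows adjustment to tolerance. A sensible investigator would reduce the dose. That stands as a reason to keep the point modest. It does not remove the point, because advisory guidance that names two different next steps for one patient is still faulty.

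A reader might infer that the cells give opposite instructions. They do not: both respond with less drug, and the left cell can also end in discontinuation. What is missing is the intermediate step, and the slip errs towards caution.

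Few patients are likely to be affected. Section 2.4.2 describes hypertension as largely manageable, and exclusion criteria 10 and 11 remove uncontrolled hypertension and patients needing two or more antihypertensives. In the neoadjuvant axitinib trial in section 2.4.3, 1 of 24 patients stopped for adverse events of any kind (4%; exact 95% interval about 0.1% to 21%), at week 7. At that rate about 2 of 50 would stop. That trial's dose rules are not shown, so this does not count patients reaching the Step 3 exit, but it suggests that early stopping is uncommon.

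**Conclusion.** The inconsistency is real and is not resolved elsewhere in the protocol. Followed as written, the algorithm ends axitinib in a non-crisis patient without a reduction being tried. It is worth correcting in the next amendment as a faulty safety instruction.

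The size is limited. The number of patients reaching this exit is not given and is probably small. The 50% to 60% of planned days missed rests on the assumed day-14 start and day-28 stop. It also overstates the contrast for any patient who would have had to stop after a reduction anyway.

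Two stronger readings are not supported. A reader might infer that the protocol compels discontinuation, but the table is only suggestive and section 6 lets a site reduce the dose. A reader might also infer harm to the rate of successful partial nephrectomy, but the document gives neither the number of patients affected nor the effect of a shortened course, so no effect on the primary outcome can be stated.

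**What to change.** In row (A), end Step 3 at the specialist referral and delete the instruction to move to row (B). Then add:

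- *Step 4. Blood pressure still not well controlled after 2 weeks: lower axitinib by one dose level (7 mg BID to 5 mg BID; 5 mg BID to a lower level that the sponsor names) and continue antihypertensives.*
- *Step 5. Stop axitinib only when severe hypertension continues after that reduction.*

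Keep row (B) for true hypertensive crisis.

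The cost is a correction to one table row, with no change to sample size, visits or endpoints. The practical burden is supply. Section 8.1 describes 5 mg tablets and section 4.1 forbids splitting them, so the sponsor must confirm a tablet strength for the level below 5 mg BID. This need is not new: the 7 mg BID dose and the cuts of about 50% in rows (F) and (H) already require other strengths. A cut of that size could serve as the lower level if it can be supplied.

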4.2 General Concomitant Medication and Supportive Care Guidelines

Patients may receive Epogen/Procrit/Aranesp for anemia as required. Anti-emetic therapy of any kind is permitted. Full transfusional support is permitted. The prophylactic use of growth factors is not allowed. The use of pyridoxine (vitamin B6) for the treatment of hand-foot syndrome is permitted.

No other approved or investigational anticancer treatment will be permitted during the study period, including chemotherapy, biological response modifiers, hormone therapy or immunotherapy. No other investigational drug may be used during treatment on this protocol, and concurrent participation in another clinical trial is not allowed.

Axitinib is metabolized primarily by liver enzymes, in particular CYP3A4. Agents known to induce CYP3A4 including dexamethasone should be avoided. Agents known to inhibit this enzyme (e.g., grapefruit juice) should also be avoided. In particular, ketoconazole should be avoided if possible, since a clinical interaction study of axitinib indicated that up to a 2-fold increase in plasma levels of axitinib was induced by ketoconazole. In addition, concomitant treatment with the following drugs with dysrhythmic potential (i.e., terfenadine, quinidine, procainamide, disopyramide, sotalol, probucol, bepridil, haloperidol, risperidone, and indapamide) is not recommended.

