- Ergot derivatives: dihydroergotamine, ergonovine, ergotamine, methylergonovine (potential increased risk for developing ergot toxicity that includes severe vasospasm leading to peripheral as well as cerebral ischemia)
- Neuroleptics: pimozide (potential increased risk for QT interval prolongation, ventricular arrhythmia, and sudden death)
- Antiarrhythmics: caution should be exercised when utilizing bepridil, flecainide, lidocaine, mexiletine, amiodarone, quinidine, propafenone (in tyrosine kinase inhibitors as a class, potential increased risk for QT interval prolongation and Torsade de Pointes; nonetheless a study by Ruiz-Garcia et al. in *Cancer Chemother Pharmacol* in 2015 noted that in healthy volunteers with Axitinib concentrations exceeded the range observed in RCC patients, axitinib was not associated with clinically significant QTc prolongation)²
- Immune modulators: cyclosporine, tacrolimus, sirolimus (potential increased risk for nephrotoxicity and neurotoxicity)
- Miscellaneous: quetiapine, risperidone, clozapine, atomoxetine.

The Effects of Other Drugs on Axitinib

Results from *in vitro* studies suggest that the oxidative metabolism of pazopanib in human liver microsomes is mediated primarily by CYP3A4/5, with minor contributions from CYP1A2 and CYP2C19.³ Furthermore, *in vitro* data suggest that axitinib is an inhibitor for p-glycoprotein. Substances that induce or inhibit CYP3A4 may alter the pharmacologic effects of pazopanib and should be used with **CAUTION**.

Medications that inhibit CYP3A4 may result in increased plasma pazopanib concentrations. Co-administration of strong CYP3A4 inhibitors is prohibited (see Section on Prohibited Medications); therefore selection of an alternate concomitant medication with no or minimal potential to inhibit CYP3A4 is recommended.

CYP3A4 inducers may decrease plasma pazopanib concentrations. Selection of an alternate concomitant medication with no or minimal enzyme induction potential is recommended. **Drugs that induce CYP3A4 and may decrease axitinib plasma concentrations include (but are not**

limited to):

- Glucocorticoids: cortisone (>50 mg), hydrocortisone (>40 mg), prednisone (>10 mg), methylprednisolone (>8 mg), dexamethasone (>1.5 mg)
- Anticonvulsants: phenytoin, carbamazepine, phenobarbital, oxcarbazepine
- HIV antivirals: efavirenz, nevirapine
- Antibiotics: rifampin (rifampicin), rifabutin, rifapentene
- Miscellaneous: St. John's Wort, modafinil, pioglitazone, troglitazone

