Prohibited Medications⁴

Subjects should not receive other anti-cancer therapy [cytotoxic, biologic, radiation, or hormonal (other than leuprolide or other GnRH agonists)] while on treatment in this study.

Medications that inhibit CYP3A4 and 1A2 inducers may result in increased plasma pazopanib concentrations; therefore, co-administration of strong CYP3A4 inhibitors is **PROHIBITED** beginning 14 days prior to the first dose of study drug until discontinuation from the study.

Strong CYP3A4 inhibitors include (but are not limited to):

- Antibiotics: clarithromycin, telithromycin, troleandomycin
- HIV: protease inhibitors (ritonavir, indinavir, saquinavir, nelfinavir, amprenavir, lopinavir)
- Antifungals: itraconazole, ketoconazole, voriconazole, fluconazole
- Antidepressants: nefazodone

References for Appendix:

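### Strong CYP3A4/5 inhibitors are allowed at about half-dose axitinib in Table 2 row F but prohibited without exception in Appendix 1, and no text says which rule governs

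*Protocol*

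**What the plan says.** Three places in the protocol deal with strong CYP3A4 inhibitors.

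- **Section 6, Table 2, row F.** Co-administration is discouraged but provided for: "Avoid coadministration if possible, if axitinib must be coadministered, decrease dose by ~50" per cent, then adjust to tolerance. The row also covers the way back: "if strong CYP3A4/5 inhibitor is discontinued, may increase to prior axitinib dose after waiting 3-5 half-lives of the inhibitor". The table is headed as suggested algorithms.
- **Section 4.2.** CYP3A4 inhibitors in general are to be avoided. The ketoconazole sentence is softer: "In particular, ketoconazole should be avoided if possible". Its reason is that "up to a 2-fold increase in plasma levels of axitinib was induced by ketoconazole". No dose change is given, and there is no pointer to row F or Appendix 1.
- **Appendix 1.** Under the effects of other drugs on axitinib: "Co-administration of strong CYP3A4 inhibitors is prohibited (see Section on Prohibited Medications". The Prohibited Medications section then applies the ban "beginning 14 days prior to the first dose of study drug until discontinuation from the study" and lists the drugs, ketoconazole among them. No exception or dose-reduction route is offered.

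**The concern.** A site cannot follow both rules. Suppose a patient needs a listed inhibitor during the 8 to 10 weeks of axitinib. A site working from Table 2 gives it, halves axitinib and records a dose modification. A site working from Appendix 1 refuses it, or records a violation if it has been given. A site that consults only Section 4.2 sees a warning about higher plasma levels but no instruction to reduce the dose.

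What is at stake is the consistency of a dosing-safety rule across a multi-institution study, and the meaning of the deviation and dose-modification records that come out of it.

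**Working it through.** No sample size, power or error-rate figure is involved, so the main check is a comparison of the texts. A little arithmetic then bounds the exposure question.

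**1. Do the rules overlap?**

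| | Table 2 row F | Section 4.2 (ketoconazole) | Appendix 1 |
|---|---|---|---|
| May it be given with axitinib? | Yes, if unavoidable | Avoid if possible | No |
| Axitinib dose if given | Cut by about 50% | Not stated | Not stated |
| Period | While on the inhibitor, plus 3-5 half-lives before re-escalation | Not stated | From 14 days before first dose to study discontinuation |
| Refers to | Nothing | Nothing | Its own list only |

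The Appendix 1 ban covers the whole axitinib period, so a patient who complies with it never reaches row F. Row F could apply only after the ban has been broken, and neither section says that this is its purpose.

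**2. What is the exposure under each rule?** Appendix 1 gives ketoconazole multipliers of 2 for AUC and 1.5 for Cmax. Relative to axitinib alone:

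- Ban followed: no inhibitor is given, so AUC and Cmax are both 1.0.
- Row F followed, assuming exposure is proportional to dose: AUC 0.5 × 2 = 1.0; Cmax 0.5 × 1.5 = 0.75.
- Ketoconazole given with axitinib unchanged, as a reader of Section 4.2 alone might do: AUC 1.0 × 2 = 2.0; Cmax 1.0 × 1.5 = 1.5.

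Neither of the two conflicting rules leads to doubled exposure. Only the third case does, and it requires a site to overlook both Section 6 and Appendix 1.

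**3. How far does that figure reach?** Appendix 1 names 3 antibiotics + 6 HIV protease inhibitors + 4 antifungals + 1 antidepressant = 14 strong inhibitors. The protocol gives an exposure figure for 1 of them, ketoconazole, and none for the other 13.

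**4. Can the half dose be given?** Section 8.1 describes 5 mg tablets only. Sections 4.1 and 8.3 forbid splitting, and Section 8.3 requires twice-daily dosing.

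- From 5 mg BID: 5 × 0.5 = 2.5 mg per dose.
- From 7 mg BID: 7 × 0.5 = 3.5 mg per dose.

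Neither can be made from whole 5 mg tablets. Nor can the planned 7 mg dose itself, so Section 8.1 may not list every strength supplied. Either way, a repaired rule must say what to do if the reduced dose cannot be made.

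**The case against.** The best defence is that both rules are protective and that most sites would let a capitalised prohibition override a table headed as suggestions. That limits the harm. It does not settle precedence: the protocol nowhere says the heading subordinates Table 2 to the appendix, and the ketoconazole sentence in the main text is also permissive. It is fair to add that Section 4.2 does not endorse half-dose use, and that its general sentence on inhibitors is firmer than the one on ketoconazole.

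A second defence is that the appendix carries leftover text from another drug, since it reasons that "Medications that inhibit CYP3A4 and 1A2 inducers may result in increased plasma pazopanib concentrations". The name is wrong, but the ban attaches to the study drug in a document titled as axitinib guidance. A site has no basis for disregarding it.

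A reader might infer more than the protocol supports:

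- **That the conflict doubles exposure shortly before surgery.** It does not. That result needs a site reading Section 4.2 alone.
- **That exclusion criterion 11 shows little blood-pressure headroom.** The criterion removes patients who already need two or more antihypertensives, so it preserves headroom among those enrolled.
- **That the ban outlasts axitinib by at least 31 days** (a 1-day hold plus 30 days to the post-nephrectomy visit). This equates study discontinuation with that visit, which Appendix 1 does not do.
- **That the washout is missing because the eligibility list omits it.** Appendix 1 states it and asks for a medication history covering the 4 weeks before screening. Repeating it in Section 4 is a matter of layout.

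**Conclusion.** The contradiction between Table 2 row F and Appendix 1 stands on the text and should be corrected. Its size is modest. The same co-prescription may be handled and recorded differently from site to site, and Section 4.2 read alone lacks a dose instruction for ketoconazole. The protocol does not give the number of patients likely to need such a drug; the setting is 50 patients treated for 8 to 10 weeks.

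Nothing in the documents supports an effect on the primary partial nephrectomy rate, on power or on error rates. The finding that row F restores AUC to about 1.0 applies to ketoconazole only and assumes exposure proportional to dose. The conflict itself does not depend on that assumption.

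**What to change.** State one rule in Appendix 1, Prohibited Medications, and replace row F and the ketoconazole sentence in Section 4.2 with pointers to it. Suggested text:

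> Strong CYP3A4/5 inhibitors are prohibited from 14 days before the first dose until the last dose of axitinib. If one becomes medically unavoidable during treatment, record a deviation and reduce axitinib by about 50%; hold axitinib if the reduced dose cannot be made from the supplied tablets without splitting. The prior dose may resume 3-5 half-lives after the inhibitor stops.

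This keeps the ban, turns row F into an explicit route for the exceptional case, gives a fixed order (reduce, and hold only if reduction is impossible) and ties the end of the ban to the end of axitinib. The sponsor could instead relax the appendix and let row F govern. That would also remove the conflict, provided one rule appears throughout and the tablet-strength question is answered.

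Minor tidying in the same amendment: repeat the 14-day washout in the Section 4 eligibility list, and correct the drug name in the Appendix 1 inhibitor sentences.

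The cost is a wording amendment with no new data collection. A few patients may need a different concomitant drug, or have axitinib reduced or held.
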